## **4.2 On-Study Research Evaluation**

This section applies only to patients enrolled into any of the treatment arms of the protocol.

- 4.2.1 Complete history and physical examination (including height, weight, vital signs and ECOG performance score) with documentation of 1) measurable disease, 2) narcotic use and pain assessment, and 3) prior therapies (surgical, radio therapeutic and cytotoxic) will be conducted prior to on-study. A complete medication history will be obtained prior to starting, including medications at base line, over the counter medications, homeopathic remedies, vitamins, and alternative therapies.
- 4.2.2 Imaging Studies (Baseline) - Every patient should have a baseline clinical evaluation with CT scan of chest, abdomen and/or pelvis for areas of known or suspected disease involvement prior to receiving treatment. In some patients an MRI may be more appropriate. FDG-PET scans are recommended but not mandatory. Baseline scans must be completed within 28 days prior to enrollment.
- 4.2.3 Laboratory Evaluation [baseline labs must be obtained within one week prior to enrollment].
- 4.2.4 Hematological Profile: CBC with differential and platelet count, prothrombin time, activated partial thromboplastin time.
- 4.2.5 Biochemical Profile: Sodium, potassium, chloride, CO2, BUN, creatinine, glucose, AST, ALT, alkaline phosphatase, bilirubin, albumin, total protein, LDH, calcium, phosphorous, magnesium, and urinalysis.
- 4.2.6 PT and PTT
- 4.2.7 EKG (baseline)
- 4.2.8 Pregnancy test for female patients of childbearing age and anatomic ability.

## **5 STUDY DESIGN / TREATMENT PLAN**

The purpose of this trial is to perform molecular profiling analysis in patients with advanced NSCLC, SCLC and thymic malignancies and offer enrollment into targeted therapy arms based on their molecular profiles. We will also be studying the frequency of *EGFR* germline mutations by enrolling patients from families with high susceptibility to lung cancer and their first-degree relatives (at the NCI only).

## 5.1 Specimen Collection

Individuals who meet the eligibility criteria for *EGFR* germline mutation testing but who do not have advanced cancer as defined in Section 3.1.1 will not undergo tumor biopsy for molecular profiling.

Patients with advanced cancer (as defined in Section 3.1.1) who meet eligibility criteria will undergo biopsy of the primary tumor or any metastatic site for molecular profiling analyses (with the exception of patients who have available archival material or patients that have previously undergone successful molecular profiling). All attempts will be made to obtain fresh tissue biopsies ~~but if this is~~ not feasible, archived paraffin blocks will be acceptable as long as there is enough ~~and adequate~~ material to perform the molecular profiling analyses described below. The adequacy of the archival tissue provided by the patient will be determined by the principal investigator ~~at each~~ participating institution in conjunction with the molecular pathology laboratories ~~performing~~ the molecular analyses. The following techniques will be used to obtain tissue samples for molecular profiling according to the location and size of the lesions:

- Core needle biopsy
- Excisional biopsies

Sample collection will be ~~performed~~ either by the interventional radiology or the surgery departments at the participating institution. Biopsies will be performed according to the standard operating procedures in place at the ~~performing~~ institution. Samples will be formalin fixed and sent to the local pathology ~~department~~ for further processing and confirmation of the histologic diagnosis. If possible, one of the ~~samples~~ will be immediately frozen to perform some of the correlative analyses described in Section 10.

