# **3 PATIENT SELECTION**

## **3.1 Eligibility criteria for initial enrollment**

- 3.1.1 Patients with histologically confirmed advanced NSCLC, SCLC and thymic malignancies for whom surgical resection or multimodality therapy with curative intent is not feasible. For patients with Stage III NSCLC, who can be encompassed by a radiation port, definitive XRT should have been performed first when possible.
- 3.1.2 Individuals who meet the eligibility criteria for *EGFR* germline mutation testing (Section 3.4) but who do not have advanced cancer as defined in 3.1.1 may enroll for *EGFR* germline mutation testing only and will not be eligible for the treatment or NOS arms.
- 3.1.3 Patients with advanced cancer must meet one of the following criteria (does not apply to first-degree relatives or individuals with pre-invasive histology enrolling only for *EGFR* germline mutation testing):
  - Patients must have biopsiable disease and be willing to undergo biopsy for molecular profiling
  - or
  - Patients must have enough and adequate archival material from a previous biopsy to perform molecular profiling analyses. The adequacy of the material provided

will be determined by the principal investigator in conjunction with the laboratories performing the molecular profiling analyses.

or

- Patients must have previously undergone a successful molecular profiling of their tumor with mutation analysis of any of the genes described in section 5.2 or ALK break apart fluorescence in situ hybridization, as part of this protocol (crossover patients) or other molecular profiling protocols such as the Lung Cancer Mutation Consortium protocol among others.

3.1.4 ~~Age  $\geq$ 18 years.~~

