### 3.2.2 Exclusion Criteria

3.2.2.1 Patients who have had major surgery, chemotherapy or radiotherapy within 2 weeks prior to entering the study or those who have not recovered from adverse events due to agents administered more than 2 weeks earlier.

3.2.2.2 Patients may not be receiving any other investigational agents or other medications for the treatment of their malignancy.

3.2.2.3 Patients with symptomatic brain metastases should be excluded from this clinical trial because of their poor prognosis and because they often develop progressive neurologic dysfunction that would confound the evaluation of neurologic and other adverse events. However, patients who have had treatment for their brain metastases and whose brain metastatic disease status has remained stable for at least 1 week after the end of brain radiation may be enrolled to undergo molecular profiling at the discretion of the principal investigator. In addition, brain metastatic disease should be stable for at least 4 weeks, before the patients can be enrolled in any of the experimental treatment arms.

3.2.2.4 Patients with any condition (e.g., gastrointestinal tract disease resulting in an inability to take oral medication or a requirement for IV alimentation, prior surgical procedures affecting absorption, or active peptic ulcer disease) that impairs their ability to swallow and retain tablets are excluded.

3.2.2.5 Any uncontrolled medical illness that precludes the patient from undergoing a biopsy for molecular profiling and / or receiving treatment under one of the experimental arms of the study should be excluded. These conditions include but are not limited to:

- Ongoing or uncontrolled, symptomatic congestive heart failure (Class III or IV as defined by the NYHA functional classification system (see [Appendix D](#)).
- Uncontrolled hypertension

- Unstable angina pectoris
- Cardiac arrhythmia
- Uncontrolled diabetes
- Uncontrolled psychiatric illness/social situations that would limit compliance with study requirements.

3.2.2.6 Patients with QTc prolongation (defined as a QTc interval equal to or greater than 500 msec) or other significant ECG abnormalities are excluded.

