## **15 STATISTICAL CONSIDERATIONS**

### **15.1 Study Design/Endpoints**

The primary objectives of this study are to determine the feasibility and efficacy of the use of molecular profile directed therapies in the treatment of advanced thoracic malignancies. The feasibility rate for the trial will be evaluated by determining the percentage of enrolled patients with a successful molecular profile determined. Efficacy will be determined by assessing if patients who have treatment assigned on the basis of their molecular profiling results will exhibit reasonable response rates to the drug selected for their particular profile.

Patients with NSCLC, SCLC, and thymic malignancies will be eligible for enrollment and each will be considered a separate cohort. In addition, on the basis of the molecular profiling results, one of 5 specific treatments could be assigned to each patient. The particular treatment assignments will be made according to a cascading schema as shown. If no profile of one of the 5 types listed is identified as being appropriate for a given patient, patients will be followed and treated in a separate 'other' (NOS) category.

With 3 disease types and 5 possible specific treatments for each, there are 15 possible treatment arms which will be under active consideration. For each of these 15, the study will be conducted as an optimal two-stage phase II trial (Simon R, Controlled Clinical Trials 10:1-10, 1989).

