## **16.5 Risk/Benefit Analysis**

As of 3/22/2016, the treatment arms of this study have been closed, but study remains open under NIH Intramural IRB for molecular profiling arm only. For adults in the molecular profiling arm, including those who become unable to consent, there is more than minimal risk in participation associated with the biopsy with the possibility of direct benefit by way of return of genetic findings that may provide additional treatment options outside of this study.

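### Section 5.1 does not settle whether a patient with adequate archival tissue is biopsied, and the primary feasibility rate pools three tissue sources with different entry tests

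*Combined protocol and SAP*

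**What the plan says.** Section 5.1 (Specimen Collection) has eligible patients with advanced cancer undergo biopsy, "with the exception of patients who have available archival material or patients that have previously undergone successful molecular profiling". No condition is attached to that exemption. The next sentence states that "All attempts will be made to obtain fresh tissue biopsies" and that, where this is not feasible, "archived paraffin blocks will be acceptable as long as there is enough" and adequate material.

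Section 3.1.3 gives three entry routes joined by a plain 'or', with no order of preference: biopsiable disease and willingness to be biopsied; archival tissue ("Patients must have enough and adequate archival material from a previous biopsy to perform molecular profiling analyses"); or an existing profile ("Patients must have previously undergone a successful molecular profiling of their tumor"). The Précis likewise lists biopsy and suitable paraffin blocks as alternatives.

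Section 16.5 says of the profiling arm, which that section describes as still open, that "there is more than minimal risk in participation associated with the biopsy".

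Section 15.1 defines the primary feasibility rate as the "percentage of enrolled patients with a successful molecular profile determined". It sets no target and makes no split by tissue source.

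**The concern.** The two sentences of 5.1 give different instructions for the same patient. Someone with biopsiable disease and adequate blocks is exempt under the first and is to be biopsied under the second. Whether that person undergoes an invasive procedure should not depend on which sentence the investigator applies.

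The same gap reaches a primary endpoint. The three tissue sources enter the feasibility rate under different conditions, and the plan neither fixes the mix nor reports it. A pooled percentage then reflects who was enrolled by which route as well as how often profiling works.

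**Working it through.** **1. The rules side by side.**

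| Patient | Exemption sentence, 5.1 | Fresh-tissue sentence, 5.1 | Section 3.1.3 |
|---|---|---|---|
| Biopsiable, no blocks | Biopsy | Biopsy | Biopsy route |
| Not biopsiable, adequate blocks | No biopsy | Blocks accepted as fallback | Archival route |
| Biopsiable, adequate blocks | Exempt | Biopsy attempted | Either route, no order |
| Already profiled | Exempt | No exemption repeated | Enters on existing profile |

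The first two rows agree. The third is a direct conflict. The fourth is settled in practice by section 5.2, which waives new profiling for these patients. No other section resolves the third row. The study calendar (section 12) marks a biopsy at screening, and its footnote to that line gives no archival exemption. Section 16.4 speaks of the biopsy as required for genetic testing. The Précis and 3.1.3 point the other way.

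**2. How each source enters the feasibility rate.**

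- Fresh biopsy: entry needs only biopsiable disease and willingness (3.1.3). Failure to obtain a profile can occur after enrollment and counts against the rate.
- Archival block: adequacy is itself an eligibility test (3.1.3), so inadequate blocks can be removed before the patient is counted.
- Already profiled: entry requires a successful profile, and 5.2 waives new profiling. Section 15.1 does not exclude these patients, so each one adds to numerator and denominator alike.

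**3. Already profiled patients: direction known, size not.** Let g be their share of enrollment and s the success rate in everyone else. Neither is in the documents, so both are assumed.

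- Pooled rate = g + (1 − g)s, which exceeds s by g(1 − s).
- g = 0.25, s = 0.80: 0.25 + 0.75 × 0.80 = 0.85, an excess of 5 points.
- g = 0.10, s = 0.90: 0.91, an excess of 1 point.
- g = 0.50, s = 0.70: 0.85, an excess of 15 points.

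For scale, at the roughly 600 patients of section 15.2 the 95% half-width at 80% is 1.96 × √(0.80 × 0.20 / 600) = 3.2 points. Section 15.2 warns that far fewer may be enrolled.

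**4. Fresh versus archival: neither known.** Let a be the share of patients with both biopsiable disease and adequate blocks, f the success rate of fresh tissue and k that of archival tissue. Only these patients are affected by the choice of sentence.

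- Fresh first, no return to blocks after a failed biopsy: exempting minus fresh-first = a(k − f). The sign depends on which source succeeds more often.
- Fresh first, blocks used after a failed biopsy (failures taken as independent): fresh-first minus exempting = a[f + (1 − f)k − k] = a·f·(1 − k). This is never negative.

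Section 5.1 does not say whether a biopsy that was done but yielded no profile counts as not feasible, so the documents do not choose between the two lines.

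**The case against.** The strongest reply is that the passages can be read together: 3.1.3 says who may enter, and 5.1 says what staff try first, with archival tissue as the permitted second choice. That may be the intent. It does not dispose of the conflict, because the unconditional exemption sits in 5.1 itself, one sentence before the fresh-tissue rule.

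A second reply is that feasibility is descriptive. Section 15.1 gives no threshold, and its feasibility-based stopping rule works on the number of patients in an arm, not on this rate. That stands: no trial decision turns on the pooled figure. It remains a primary objective, however, and should be reported in a form that can be interpreted.

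Three stronger readings are tempting, and the documents support none of them.

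- A reader might infer that the wording moves the feasibility rate by many points. Take assumed values a = 0.5, f = 0.80, k = 0.98, with all other patients on fresh tissue. Exempting gives 0.5 × 0.98 + 0.5 × 0.80 = 89.0%. Fresh-first without fallback gives 80.0%. With fallback it gives 0.5 × (0.80 + 0.20 × 0.98) + 0.5 × 0.80 = 89.8%. The large gap comes from switching the fallback off; with it on, the gap is 0.8 points the other way. A count of avoidable biopsies cannot be given either, because the share of patients with both sources is not stated.
- A reader might infer that section 3.2.2.5, which bars from the treatment arms "Any uncontrolled medical illness that precludes the patient from undergoing a biopsy for molecular profiling" and/or from receiving treatment, also distorts feasibility. It does not: profiled patients not placed in an arm go to the NOS arm (5.5) and stay in the denominator. Several of its listed illnesses would bear on treatment in any case, so the number barred only for biopsy is unknown.
- A reader might infer continuing differences between sites or continuing loss of patients to the arms. The participating site closed on 02/05/2015 (4.1.2), and the treatment arms stopped recruiting on 3/22/16 (5.3).

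**Conclusion.** The point holds in two parts. First, sections 5.1 and 3.1.3 do not determine whether a patient with both biopsiable disease and adequate blocks is biopsied; this is still live, since the profiling arm is described as open. Second, the feasibility rate combines sources with unequal entry tests, so one pooled figure cannot be interpreted as the feasibility of profiling.

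Previously profiled patients can only raise the rate, by 1 to 15 points over the assumed ranges above. This takes 15.1 at its word that all enrolled patients count. For fresh against archival tissue, no size or direction can be claimed. The biopsy clause of 3.2.2.5 is a secondary ambiguity and now historical.

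**What to change.** - Reconcile the two sentences of 5.1 with 3.1.3, and bring the Précis, the calendar and 16.4 into line, so that one tissue sequence applies. State whether archival tissue may be used after a biopsy that yields no profile. Which sequence to adopt is for the investigators; this point does not prescribe one.
- In 15.1, report feasibility overall and by source (fresh biopsy, archival block, previously profiled), with the denominator of each row stated, and report the rate again with previously profiled patients excluded.
- As a secondary clarification, record whether the biopsy clause of 3.2.2.5 was applied to patients who needed no biopsy.

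The cost is wording, one extra table and possibly a less favourable rate once previously profiled patients are set aside. No added patients or procedures are needed, and the table can still be produced for those already enrolled.

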## 5.2 Molecular Profiling

After the tumor samples are obtained, molecular profiling analyses will be performed to determine enrollment in specific treatment arms (with the exception of patients who have previously undergone successful molecular profiling). ~~Since~~ these analyses will be used for treatment decisions, they will be performed in a CLIA certified laboratory at the participating institutions. The following is a list of the molecular profiling analyses to be performed:

### 5.2.1 Gene mutation analyses for treatment decisions

Approved Gene Symbol	Approved Gene Name	Location	Sequence Accession IDs	Previous Symbols	Aliases
AKT1	v-akt murine thymoma viral oncogene homolog 1	14q32.32-q32.33	M63167 NM_005163		RAC, PKB, PRKBA, AKT
AKT2	v-akt murine thymoma viral oncogene homolog 2	19q13.1-q13.2	NM_001626		
BRAF	v-raf murine sarcoma viral oncogene homolog B1	7q34	M95712 NM_004333		BRAF1
EGFR	epidermal growth factor receptor (erythroblastic leukemia viral (v-erb-b) oncogene homolog, avian)	7p12	NM_005228	ERBB	ERBB1

ERBB2	v-erb-b2 erythroblastic leukemia viral oncogene homolog 2, neuro/glioblastoma derived oncogene homolog (avian)	17q11.2-q12	X03363	NGL	NEU, HER-2, CD340, HER2
HRAS	v-Ha-ras Harvey rat sarcoma viral oncogene homolog	11p15.5	AJ437024 NM_176795	HRAS1	
KIT	v-kit Hardy-Zuckerman 4 feline sarcoma viral oncogene homolog	4q11-q12	S67773	PBT	CD117, SCFR, C-Kit
KRAS	v-Ki-ras2 Kirsten rat sarcoma viral oncogene homolog	12p12.1	BC010502 NM_033360	KRAS2	KRAS1
NRAS	neuroblastoma RAS viral (v-ras) oncogene homolog	1p13.2	BC005219 NM_002524		
PDGFRA	platelet-derived growth factor receptor, alpha polypeptide	4q12	D50001 NM_006206		CD140a, PDGFR2
PIK3CA	phosphoinositide-3-kinase, catalytic, alpha polypeptide	3q26.3	NM_006218		p110-alpha, MGC142161, PI3K, MGC142163
PTEN	phosphatase and tensin homolog	10q23	U92436 NM_000314	BZS, MHAM	MMAC1, TEP1, PTEN1

### 5.2.2 ERBB2 amplification by FISH

### 5.2.3 PDGFRA amplification by FISH

[figure not shown]
## 5.3 Enrollment in treatment arms

**Treatment arms are no longer recruiting as of 3/22/16.**

Due to the rapidly progressing course of the thoracic malignancies in this study, treatment decisions will be made in approximately 2 weeks from the time that the tumor samples were obtained. Based on the molecular profiling results, the patients will be offered enrollment into a specific treatment arm according to the decision tree shown in [Figure 2](#) and the eligibility criteria described in [Section 3](#).

Individuals who meet the eligibility criteria for *EGFR* germline mutation testing ([Section 3.4](#)) but who do not have advanced cancer as defined in [Section 3.1.1](#) are not eligible for the treatment arms.

Figure 2. Schema

\* See Sections 3.2 and 3.3 for eligibility criteria for the treatment arms. Patients will be allowed to crossover to different treatment arms as long as they meet eligibility criteria.

† See separate eligibility criteria (Section 3.4) and schema for EGFR germline mutation testing.

No = No or not available

Amp = gene amplification by FISH

NOS = non-otherwise specified arm

**A** = optional re-biopsy for patients that responded to previous line of therapy

Each study arm is independent from the other arms; it has its own eligibility criteria (Section 3) and statistical considerations (Section 15), and will be analyzed independently. Additionally, it is not our intention to compare the outcomes among treatment arms since the patients enrolled in each arm will have different molecular characteristics.

Patients enrolled in one of the treatment arms of this protocol, with the exception of the NOS arm and individuals enrolled for EGFR germline mutation testing only, will be treated and

followed with clinical visits at least every 3, 4, or 6 weeks, as defined for each treatment arm; i.e., every 3 weeks for the Erlotinib, AZD6244, and Lapatinib arms; every 4 weeks for the MK-2206 arm; and every 6 weeks for the Sunitinib arm. The time between clinic visits may be extended at the PI's discretion by up to 1 full cycle, for a maximum of 2 cycles between clinic visits (i.e., clinic visits may be extended to every 6 weeks for the Erlotinib, AZD6244, and Lapatinib arms; every 8 weeks for the MK-2206 arm; and every 12 weeks for the Sunitinib arm). If the frequency of clinic visits is extended, laboratory tests will not be required nor samples collected until the next clinic visit. Re-staging imaging will be performed at the end of every two cycles as defined for each treatment arm; i.e., every 6, 8, or 12 weeks +/- 1 week. See Section 5.9.2 for details. The patients will continue on the selected arms until disease progression.

#### **5.4 Treatment after disease progression**

Patients who initially had a response to treatment or a prolonged stabilization of the tumor (>6 months) but that eventually develop progressive disease, will be offered the option to have a repeat biopsy for molecular profiling analyses. This biopsy will have the intention to study potential mechanisms of resistance to specific targeted therapies. This will also be potentially used for treatment decisions or enrollment in other molecularly targeted protocols. However, if the patient refuses this option, we will use the most recent results of the molecular profiling analyses to verify eligibility for enrollment in an alternative treatment arm on this study (crossover).

At the time of disease progression, the patients will be allowed to re-register onto another treatment arm that is available in this protocol, according to the schema, and as long as they still meet the eligibility criteria described in Section 3. In this case, patients will be re-registered onto the treatment arm, but not re-consented. The patient will count as a new patient to that specific arm, keeping their original patient ID number.

